### Screening Phase

- Begins by establishing the subject's initial eligibility and signing of the informed consent form (ICF).
- Subject is enrolled using the Interactive Response Technology (IRT) system.

- The choice of chemotherapy regimen XELOX or FOLFOX must be decided before placing the randomization call to the IRT system.
- Subjects must have PD-L1 immunohistochemistry (IHC) testing, with results, performed by the central lab during the Screening period. Without evaluable PD-L1 result, the subject may not be randomized.
- Subject is assessed for study eligibility according to the inclusion and exclusion criteria. All screening assessments and procedures must be performed within 28 days prior to randomization unless otherwise specified.

### **Treatment Phase**

- Begins after the randomization call to the IRT system. The subject is randomly assigned in a 1:1:1 ratio to the nivo+chemo, nivo+ipi or the chemo arm up to protocol amendment 20. After amendment 20, the subject is randomized to 1:1 the nivo+chemo or the chemo arm as enrollment to nivo+ipi was closed.
- Administration of study treatment is to begin within 3 calendar days of randomization.
- The treatment phase ends when the subject is discontinued from study therapy.
- Treated subjects will be evaluated for tumor assessments every 6 weeks ( $\pm 7$  days) up to and including Week 48, then every 12 weeks ( $\pm 7$  days) thereafter.

### **Dosing in the Nivo+Ipi Arm:**

- On the day of infusion, nivolumab is to be administered first. The second infusion will always be ipilimumab, and will start at least 30 minutes after completion of the nivolumab infusion.
- Nivolumab (as flat dose) is allowed to be administered alone in case ipilimumab has to be discontinued due to toxicity. Ipilimumab is also allowed to be administered alone in case nivolumab has to be discontinued due to toxicity.
- Treatment beyond initial, investigator-assessed, RECIST 1.1-defined progression is permitted if the subject has investigator-assessed clinical benefit and is tolerating treatment.

### **Dosing in the Nivo+Chemo Arm:**

- On the day of infusion, nivolumab is to be administered first. The administration procedures of chemotherapy will follow local standards.
- Nivolumab is allowed to be administered alone in case the chemotherapy has to be discontinued due to toxicity. Chemotherapy alone is also allowed to be administered in doublet or monotherapy in case nivolumab has to be discontinued due to unacceptable toxicity.
- Nivolumab treatment beyond initial, investigator-assessed, RECIST 1.1-defined progression is permitted if the subject has investigator-assessed clinical benefit and is tolerating treatment. Chemotherapy alone is not allowed to treat beyond progression.

- No cross-over is allowed between XELOX and FOLFOX.

### **Dosing in the Chemo Arm:**

- The administration procedures will follow local standards.
- No cross-over is allowed between XELOX and FOLFOX.

### **Follow-up Phase**

- Begins when the decision is made to discontinue a subject from study therapy.
- After completion of the first 2 follow-up (FU) visits (30 days [ $\pm$  7 days] from last dose and 84 days [ $\pm$  7 days] from FU1), subjects will be followed by clinic visit or phone contact every 3 months ( $\pm$ 14 days) or more frequently as needed for survival status and subsequent anti-cancer therapy.
- Subjects who discontinue treatment for reasons other than PD will continue to have tumor assessments (until PD) every 6 weeks ( $\pm$  7 days) up to and including Week 48, then every 12 weeks ( $\pm$ 7 days) thereafter.
- Subjects will be followed for drug-related toxicities until these toxicities resolve, return to baseline or are deemed irreversible. All drug-related toxicities will be documented for a minimum of 100 days after the last dose of study drug.

## **2.2 Treatment Assignment**

After the subject's initial eligibility is established and informed consent has been obtained, the subject must be enrolled into the study by entering information into the IRT system to obtain the subject number. Every subject that signs the ICF must be assigned a subject number in the IRT.

Once enrolled in the IRT, subjects that have met all eligibility criteria (the required tumor tissue received and result obtained by the central laboratory) will be ready to be randomized through the IRT.

Randomization will be stratified by the following factors:

- PD-L1 expression level (tumor cells) ( $\geq$  1% vs.  $<$  1% or indeterminate)
- Region: Asia vs. US vs. RoW
- ECOG performance status: 0 vs. 1
- Planned chemotherapy regimen (XELOX vs. FOLFOX)\*

\* Chemotherapy was added as a randomization stratification factor with Amendment 08. Information has been collected in IRT even for subjects randomized prior to amendment 08.

### 2.3 Blinding and Unblinding

The trial is open label, however the Sponsor will handle the study as a blinded study and no analyses or summaries by randomized treatment arms will be produced during the conduct of the study by the Sponsor.

The final PFS analysis in randomized subjects with PD-L1 CPS  $\geq 5$  and interim OS analyses in randomized subjects with PD-L1 CPS  $\geq 5$  will be reviewed by the Data Monitoring Committee (DMC). The DMC will also review interim OS analyses in randomized subjects with PD-L1 CPS  $\geq 1$  and the interim OS analysis in all randomized subjects. The analyses, by unblinded arms, will be provided by the DMC independent reporting statistician to the DMC members.

If the formal efficacy interim analysis meets the pre-specified statistical criteria for at least one of the primary endpoints (PFS in PD-L1 CPS  $\geq 5$  or OS in PD-L1 CPS  $\geq 5$ ), the DMC Chairman will notify the BMS Head of Oncology Clinical Development by releasing the DMC closed report with unblinded treatment arms. The BMS Head of Oncology Clinical Development may in turn choose to release the closed report to additional members of the BMS restricted team after reviewing the closed DMC report. The BMS Head of Oncology Clinical Development will inform the DMC members and the independent statistician by email on whether the restricted BMS team has decided that the BMS study team should be unblinded to the study results.

The closed report, which will be shared with the BMS restricted team, will only contain the aggregated OS results by treatment arms for the CPS cutoffs which meet statistical significance. It will not contain OS results for the CPS cutoffs that do not meet statistical significance unless it is requested by health authorities. The PFS results will be included in the closed report if at least one of the PFS endpoint and OS endpoint meets statistical significance as this is the final and unique analysis for PFS.

In addition, the Blinded Independent Central Review (BICR) Committee will perform the central imaging review without knowledge of the treatment group assignment.

The Lab vendor performing the tumor cell PD-L1 and CPS PD-L1 scoring is also blinded to the treatment group assignment.

### 2.4 Protocol Amendments

Global amendments incorporated in the protocol with relevant changes are described in Table 2.4-1.

**Table 2.4-1: Relevant Protocol Amendments**

Amendments	Date of Issue	Summary of Major Changes
Amendment 29	16-sep-2019	
 
Based on the data from the Keynote 062 study, PFS and OS Kaplan-Meier curves showed an observed delayed separation, the timing of PFS and OS analyses are updated with minimum follow up 12 and 24 months. In addition, to reduce variability of efficacy results, PFS population was expanded to all randomized subjects with PD-L1 CPS <math>\geq 5</math>.
 

**Table 2.4-1: Relevant Protocol Amendments**

Amendments	Date of Issue	Summary of Major Changes
		
 
A 480mg Q4W nivolumab dosing option for subjects who receive nivolumab alone after treatment with nivolumab in combination with ipilimumab or FOLFOX/XELOX is allowed.
 

Amendment 26	15-Nov-2018	
 
Based on recent internal data, added approximately 356 subjects into randomization, in total of approximately 2005 subjects will be randomized to keep sample size for primary analyses of PFS and OS in PD-L1 CPS <math>\geq</math> 5 subjects for nivolumab in combination with chemotherapy vs. chemotherapy.
 

Amendment 23	14-Sep-2018	
 
Incorporates the combined positive score (CPS) for PD-L1 expression, the primary population is now subjects with PD-L1 expression <math>\geq</math> 5 by CPS rather than by the tumor proportion score (TPS) for subjects with nivolumab in combination with oxaliplatin and fluoropyrimidine compared to oxaliplatin and fluoropyrimidine.
 
The planned analysis of overall survival (OS) for nivolumab plus ipilimumab arm is changed to a secondary objective.
 
Objective response rate (ORR) has been changed to a secondary endpoint.
 
The primary, secondary, and exploratory objectives have been updated to reflect changes in subject population definition.
 
Second disease progression (PFS2) and time to secondary subsequent therapy (TSST) have been added as exploratory analyses.
 
Statistical assumptions and considerations revised to reflect changes in study population and revised objectives.
 

Amendment 20	11-Jun-2018	
 
Per recommendation of the Data Monitoring Committee (DMC), as of 05-June-2018, the nivolumab plus ipilimumab arm is now closed. Subjects randomized to this arm prior to or on 05-June-2018 will continue to receive treatment with study drugs per protocol, and the study data will remain blinded until planned primary analysis.
 

Amendment 19	29-May-2018	
 
Added that randomization of an additional 300 subjects beyond the originally planned 1349 subjects across the 3 study arms will allow for more robust analysis of the treatment effect of nivolumab in combination with ipilimumab or chemotherapy across different PD-L1 cutoffs in 1L GC/GEJ cancer.
 

Amendment 08	07-Dec-2016	
 
Added a new randomization arm, N+C to the study.
 
Added chemotherapy as randomization stratification factor.
 
Added Blinded Independent Central Review (BICR) of tumor images.
 
Clarified some study procedures, including limiting the treatment period with nivolumab to 2 years.
 

## 2.5 Blinded Independent Central Review of Progression

The clinical management of subjects during the study will be based upon local radiologic tumor measurements. Tumor assessments for each subject should be submitted to the radiology vendor as they are performed, on an ongoing basis. The blinded, independent radiologists will review all available tumor assessments for that given subject and determine if RECIST 1.1 criteria for progression have been met.

If clinically acceptable, subsequent therapy should begin only after RECIST 1.1 progression has been assessed by blinded independent central review. When RECIST 1.1 progression is assessed by the investigator (whether assessed before or after the start of subsequent therapy), confirmation by the BICR must be requested. Tumor assessments may be discontinued when the independent radiologist assesses the subject to have met RECIST 1.1 criteria for progression.

In addition, subjects receiving treatment beyond progression must continue tumor assessments until treatment has been discontinued.

## 2.6 Data Monitoring Committee

An independent DMC will be utilized to provide oversight of safety and efficacy considerations. Additionally, the DMC will provide advice to the sponsor regarding actions the committee deems necessary for the continuing protection of subjects enrolled in the study. The DMC will be charged with assessing such actions in light of an acceptable benefit/risk profile for nivolumab plus ipilimumab and nivolumab plus chemotherapy. The DMC will act in an advisory capacity to BMS and will monitor subject safety and evaluate the available efficacy data for the study. The oncology therapeutic area of BMS has primary responsibility for design and conduct of the study.

The DMC will also be responsible for conducting formal interim efficacy analysis of the study for final PFS analysis and interim analysis of OS for nivo + chemo vs. chemo.

## 3 OBJECTIVES

### 3.1 Primary

**Nivolumab in combination with oxaliplatin plus fluoropyrimidine vs. oxaliplatin plus fluoropyrimidine:**

To compare OS in subjects with advanced or metastatic GC or GEJ cancer with PD-L1 CPS  $\geq 5$ .

To compare PFS, as assessed by BICR in subjects with advanced or metastatic GC or GEJ cancer with PD-L1 CPS  $\geq 5$ .

### 3.2 Secondary

**Nivolumab plus ipilimumab vs. oxaliplatin plus fluoropyrimidine:**

- To compare OS in subjects with advanced or metastatic GC or GEJ cancer with PD-L1 CPS  $\geq 5$  or all randomized subjects.
- To compare the time to symptom deterioration (TTSD) as assessed using the Gastric Cancer Subscale (GaCS) of the Functional Assessment of Cancer Therapy-Gastric (FACT-Ga) in

subjects with advanced or metastatic GC or GEJ cancer with PD-L1 CPS  $\geq 5$  or all randomized subjects.

- To evaluate OS in subjects with advanced or metastatic GC or GEJ cancer with PD-L1 CPS  $\geq 10$  or subjects with PD-L1 CPS  $\geq 1$ .
- To evaluate PFS, as assessed by BICR, in subjects with advanced or metastatic GC or GEJ cancer with PD-L1 CPS  $\geq 10, 5, 1$  or all randomized subjects.
- To evaluate ORR, as assessed by BICR, in subjects with advanced or metastatic GC or GEJ cancer with PD-L1 CPS  $\geq 10, 5, 1$  or all randomized subjects.

**Nivolumab in combination with oxaliplatin plus fluoropyrimidine vs. oxaliplatin plus fluoropyrimidine:**

- To compare OS in subjects with advanced or metastatic GC or GEJ cancer with PD-L1 CPS  $\geq 1$  or all randomized subjects
- To evaluate OS in subjects with advanced or metastatic GC or GEJ cancer with PD-L1 CPS  $\geq 10$ .
- To evaluate PFS, as assessed by BICR, in subjects with advanced or metastatic GC or GEJ cancer with PD-L1 CPS  $\geq 10, 1$  or all randomized subjects.
- To evaluate ORR, as assessed by BICR, in subjects with advanced or metastatic GC or GEJ cancer with PD-L1 CPS  $\geq 10, 5, 1$ , or all randomized subjects.

**3.3 Exploratory**

**Nivolumab in combination with oxaliplatin plus fluoropyrimidine vs. oxaliplatin plus fluoropyrimidine:**

- To assess TTSD using GaCS of FACT-Ga in subjects with advanced or metastatic GC or GEJ cancer with PD-L1 CPS  $\geq 5$  or all randomized subjects.

**For both comparisons: Nivolumab in combination with oxaliplatin plus fluoropyrimidine vs. oxaliplatin plus fluoropyrimidine and Nivolumab plus ipilimumab vs. oxaliplatin plus fluoropyrimidine:**

- To assess PFS and ORR, as assessed by the investigator in subjects with advanced or metastatic GC or GEJ cancer across PD-L1 CPS cut-offs.
- To evaluate Duration of Response (DOR) as assessed by BICR and by investigator, in subjects with advanced or metastatic GC or GEJ.
- To evaluate the durable response rate (DRR) (defined as objective response lasting continuously  $> 6$  months) as assessed by BICR and by investigator, in subjects with advanced or metastatic GC or GEJ cancer.
- To evaluate at 18, 24, and 36 months survival rates in subjects with advanced or metastatic GC or GEJ cancer.

- To evaluate second disease progression (PFS2) or time to second subsequent therapy (TSST) in subjects with advanced or metastatic GC or GEJ cancers.
- To assess PFS, ORR as assessed by either BICR or investigator, OS in subjects with advanced or metastatic GC or GEJ cancer across PD-L1 tumor proportion score (TPS) cut-offs.
- To assess the overall safety and tolerability of nivolumab plus ipilimumab or nivolumab in combination with oxaliplatin plus fluoropyrimidine and oxaliplatin plus fluoropyrimidine in subjects with advanced or metastatic GC or GEJ cancer.
- To explore potential biomarkers predictive of or associated with clinical efficacy (OS, PFS and ORR) and/or incidence of AEs of nivolumab plus ipilimumab or nivolumab in combination with oxaliplatin plus fluoropyrimidine including but not limited to microsatellite instability (MSI) status, tumor mutational burden (TMB), [REDACTED] [REDACTED] [REDACTED] [REDACTED] and inflammatory signatures in subjects with advanced or metastatic GC or GEJ cancer.
- To assess TTSD as assessed using GaCS of FACT-Ga in subjects with advanced or metastatic GC or GEJ cancer with PD-L1 CPS  $\geq 10$ , or 1.
- To assess changes from baseline in the subject's overall health status using the 3-level version of the EQ-5D (EQ-5D-3L) index and visual analog scale (EQ-VAS).
- To assess the subject's cancer-related quality of life using the FACT-Ga questionnaire and selected components, including the GaCS and 7-item version of the FACT-General (FACT-G7).

#### 4 ENDPOINTS

A summary of the efficacy endpoints is presented in Table 4-1

**Table 4-1: Summary of Key Efficacy Endpoints**

	Nivolumab plus Chemotherapy vs Chemotherapy	Nivolumab plus Ipilimumab vs Chemotherapy
Primary endpoints	
 
• PFS by BICR in subjects with PD-L1 CPS <math>\geq 5</math> (controlled for Type I error)
 
• OS in subjects with PD-L1 CPS <math>\geq 5</math> (controlled for Type I error)
 
	
Secondary endpoints	
 
• OS in subjects with PD-L1 CPS <math>\geq 1</math>, and in all randomized subjects (controlled for Type I error)
 
• OS in subjects PD-L1 CPS <math>\geq 10</math>
 
• PFS by BICR in subjects with PD-L1 CPS <math>\geq 10</math>, 1 or all randomized subjects
 
	
 
• OS in subjects with PD-L1 CPS <math>\geq 5</math> and in all randomized subjects. (controlled for Type I error)
 
• OS in subjects PD-L1 CPS <math>\geq 10, 1</math>
 
• ORR, PFS by BICR in subjects with PD-L1 CPS <math>\geq 10, 5, 1</math> or all randomized subjects.
 
• TTSD in subjects with PD-L1 CPS <math>\geq 5</math> and in all randomized subjects (controlled for Type I error)
 

**Table 4-1: Summary of Key Efficacy Endpoints**

	Nivolumab plus Chemotherapy vs Chemotherapy	Nivolumab plus Ipilimumab vs Chemotherapy
Exploratory Endpoints	
 
• ORR by BICR in subjects with PD-L1 CPS <math>\geq</math> 10, 5, 1 or all randomized subjects
 
• ORR, PFS by investigator in subjects with PD-L1 CPS <math>\geq</math> 10, 5, 1 or all randomized subjects
 
• OS, PFSa, ORRb in subjects with PD-L1 TPS across cut-offs
 
• OS rates at 18, 24, and 36 months
 
• PFS 2 or TSST on next line treatment
 
• DOR
 
• DRR
 
• TTSD in subjects with PD-L1 CPS <math>\geq</math> 10, 5, 1 or all randomized subjects
 
• Biomarkers
 
	
 
• ORR, PFS by investigator in subjects with PD-L1 CPS <math>\geq</math> 10, 5, 1 or all randomized subjects
 
• OS, PFSc, ORRd in subjects with PD-L1 TPS across cutoffs
 
• OS rates at 18, 24, and 36 months
 
• PFS 2 or TSST on next line treatment
 
• DOR
 
• DRR
 
• TTSD in subjects with PD-L1 CPS <math>\geq</math> 10, or 1
 
• Biomarkers
 

a Per BICR and investigator assessments

## 4.1 Primary Endpoints for Nivolumab plus Chemotherapy

For nivo+chemo versus chemo.

### 4.1.1 Overall Survival

Overall Survival is defined as the time from the date of randomization to the date of death from any cause. For subjects that are alive, their survival time will be censored at the date of last contact date (or “last known alive date”). Overall survival will be censored at the date of randomization for subjects who were randomized but had no follow-up.

Primary objective of the study is the comparison of OS between nivo+chemo and chemo in PD-L1 CPS  $\geq$  5 subjects.

### 4.1.2 Progression-Free Survival

Two definitions are used for analysis of Progression-Free Survival. The primary definition accounts for subsequent therapy by censoring at the last evaluable tumor assessment on or prior to the date of subsequent therapy. This definition will be used to run the primary analysis of PFS (per BICR) for this trial and to declare statistical significance for the PFS endpoint.

The secondary definition is irrespective of subsequent therapy and will be presented as supportive analysis of the primary PFS analysis. This definition is considered primary by EMA.

Clinical deterioration in the absence of unequivocal evidence of progression (per RECIST v1.1 criteria) is not considered progression for purposes of determining PFS.

PFS rates at fixed time points (eg, 6 months, depending on the minimum follow-up) are defined as the probability that a subject has not progressed and is alive at time  $T$  following randomization.

The first on-study tumor assessment is scheduled to be conducted at 6 weeks ( $\pm 1$  week) following first dose. Subsequent tumor assessments are scheduled every 6 weeks ( $\pm 1$  week) up to and including Week 48, then every 12 weeks ( $\pm 7$  days) regardless of treatment schedule until disease progression.

#### **4.1.2.1 Primary Definition of Progression-Free Survival (Accounting for Subsequent Therapy)**

The primary definition of PFS (PFS truncated at subsequent therapy) is defined as the time between the date of randomization and the date of first documented tumor progression, based on BICR assessments (per RECIST v1.1 criteria), or death due to any cause, whichever occurs first.

The following censoring rules will be applied for the primary definition of PFS:

- Subjects who did not progress or die will be censored on the date of their last evaluable tumor assessment.
- Subjects who did not have any on-study tumor assessments and did not die will be censored on their date of randomization.
- Subjects who received subsequent anti-cancer therapy prior to documented progression will be censored at the date of the last evaluable tumor assessment conducted on or prior to the date of initiation of the subsequent anti-cancer therapy.
- Subjects who did not have a documented progression and received subsequent anti-cancer therapy will be censored at the date of the last evaluable tumor assessment conducted on or prior to the initiation of the subsequent anti-cancer therapy.

In the above, subsequent anti-cancer therapy is all systemic therapies, surgery with reason of tumor resection palliative or tumor resection curative, radiotherapy with reason curative or palliative.

Censoring rules for the primary definition of PFS (PFS truncated at subsequent therapy) are presented in [Figure 4.1.2.1-1](#) and in [Table 4.1.2.1-1](#).

Figure 4.1.2.1-1: PFS Primary Definition

[figure not shown]

Table 4.1.2.1-1: Censoring Scheme Used in Primary Definition of PFS

Situation	Date of Progression or Censoring	Outcome
No baseline tumor assessments*	Date of randomization	Censored
No on study tumor assessments and no death*	Date of randomization	Censored
Subsequent anti-cancer therapy started without prior progression per RECIST v1.1 or death	Date of last evaluable tumor assessment prior to or on the date of initiation of the subsequent anti-cancer therapy	Censored
Documented progression per RECIST v1.1 and no subsequent anti-cancer therapy started before	Date of the first documented progression per RECIST v1.1 (excludes clinical progression)	Progressed
No progression and no death, and no new anti-cancer therapy started	Date of last evaluable tumor assessment	Censored
Death without progression per RECIST v1.1 and no prior subsequent anti-cancer therapy	Date of death	Progressed

\* Tumor assessments and death if any, occurring after start of subsequent anti-cancer therapy are not considered.

Primary objective of the study is the comparison of PFS between nivo+chemo and chemo in PD-L1 CPS  $\geq 5$  subjects.

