8.3.1 Primary Efficacy Measures

Overall survival (OS). OS is defined as the time between the date of randomization and the date of death. For subjects without documentation of death, OS will be censored on the last date the subject was known to be alive.

Progression-free Survival (PFS) as assessed by BICR is defined as the time from randomization to the date of the first documented PD per BICR or death due to any cause. Subjects who die without a reported prior PD per BICR (and die without start of subsequent therapy) will be considered to have progressed on the date of death. Subjects who did not have documented PD per BICR per RECIST1.1 criteria and who did not die, will be censored at the date of the last evaluable tumor assessment on or prior to initiation of subsequent anti-cancer therapy. Subjects who did not have any on-study tumor assessments and did not die (or died after initiation of subsequent anti-cancer therapy) will be censored at the randomization date. Subjects who started any subsequent anti-cancer therapy without a prior reported PD per BICR will be censored at the last tumor assessment prior to or on the initiation of the subsequent anti-cancer therapy.

The same definition will be used for OS and PFS for nivolumab plus ipilimumab, which are secondary endpoints.

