**Table 4.1.2.2-1: Censoring Scheme for Secondary Definition of PFS**

Situation	Date of Progression of Censoring	Outcome
No baseline tumor assessment	Date of randomization	Censored
No on-study tumor assessments and no death	Date of randomization	Censored
Documented progression per RECIST v1.1	Date of first documented progression per RECIST v1.1 criteria (excludes clinical progression)	Progressed
No progression and no death	Date of last evaluable tumor assessment	Censored
Death without progression per RECIST v1.1	Date of death	Progressed

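### The missing-baseline row in both SAP PFS censoring tables has no death condition, so it overlaps the death row with the opposite outcome and no stated precedence

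*SAP*

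**What the plan says.** **Primary definition, SAP Table 4.1.2.1-1.** The first row, "No baseline tumor assessments", gives censoring at the randomization date. The second row, "No on study tumor assessments and no death", gives the same outcome but only for subjects who have not died. The last row, "Death without progression per RECIST v1.1 and no prior subsequent anti-cancer therapy", gives an event on the date of death. The first two rows carry a footnote: "Tumor assessments and death if any, occurring after start of subsequent anti-cancer therapy are not considered".

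**Secondary (ITT) definition, SAP Table 4.1.2.2-1.** The first row, "No baseline tumor assessment", again censors at randomization with no condition on death. The last row, "Death without progression per RECIST v1.1", makes the death an event. This table has no footnote.

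**SAP text rules, Section 4.1.2.1.** Only one rule leads to censoring at randomization: "Subjects who did not have any on-study tumor assessments and did not die will be censored on their date of randomization". Neither 4.1.2.1 nor 4.1.2.2 has a text rule for a missing baseline.

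**Protocol 8.3.1.** A subject who dies with no earlier BICR progression and no subsequent therapy "will be considered to have progressed on the date of death". No exception is made for a missing baseline.

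**The concern.** The two tables are what a programmer would code from. A subject with no baseline assessment who dies without documented progression (and, for the primary definition, before subsequent therapy) meets the conditions of both the first and the last row. One row gives a censored time of zero and the other gives an event at death.

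If the first row is evaluated first, a known death leaves a primary endpoint and the subject contributes no follow-up at all. The protocol definition and the SAP's own text rules do not allow that. The secondary definition is exposed too. SAP 4.1.2 says the EMA treats that definition as primary, and its purpose is to ignore intercurrent therapy and count every death without prior progression.

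The unqualified category is not confined to the tables. SAP 7.5.2.1 and 7.5.3.5 list a missing baseline as a censoring reason, separately from the category for no on-study assessment and no death.

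**Working it through.** **Step 1. Compare the rules for one subject: no baseline assessment, no documented progression, death before any subsequent therapy.**

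| Source | Outcome |
|---|---|
| Protocol 8.3.1 | Event at death |
| SAP 4.1.2.1 text | Event at death; the randomization-date rule requires that the subject did not die |
| SAP Table 4.1.2.1-1, first row | Censored at randomization |
| SAP Table 4.1.2.1-1, last row | Event at death |
| SAP Table 4.1.2.2-1, first row | Censored at randomization |
| SAP Table 4.1.2.2-1, last row | Event at death |

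Each table gives two answers. The protocol and the SAP text give one.

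**Step 2. Reproduce the planned PFS power.** Inputs from SAP Appendix 5, Table 1: 949 subjects, two-sided alpha 0.02, 841 events with average HR 0.66 (3-month delay), 857 events with average HR 0.80 (6-month delay). Schoenfeld with 1:1 allocation: power = Φ(½·√D·|ln HR| − 2.326).

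- D = 841, HR 0.66: ½ × 29.00 × 0.4155 − 2.326 = 3.70, so 99.99% (SAP: 99.9%).
- D = 857, HR 0.80: ½ × 29.27 × 0.2231 − 2.326 = 0.94, so 82.6% (SAP: 84.0%, by simulation).

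Both are within 2 points of the SAP figures.

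**Step 3. Deaths at stake.** The documents do not say how many subjects lack a baseline. Assumed range: 0.5% to 2% of 949, which is 4.7 to 19.0 subjects. SAP Appendix 5, Table 2 expects 680 deaths among 949 at the first analysis: 680/949 = 71.7%.

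- Low: 4.7 × 0.717 = 3.4 deaths; 3.4/857 = 0.4% of events.
- High: 19.0 × 0.717 = 13.6 deaths; 13.6/841 = 1.6% of events.

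This gives about 3 to 14 events, if the first row always prevails. For the primary definition it overstates the loss, because the 680 include deaths after subsequent therapy, which both documents intend to leave out.

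**Step 4. Effect on power in the 6-month-delay case.** Two losses larger than 14 are used as harder tests:

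- 2% of 857 events (17) lost, D = 840: ½ × 28.98 × 0.2231 − 2.326 = 0.907, so 81.8%.
- All 19 subjects die and all 19 events are lost, D = 838: ½ × 28.95 × 0.2231 − 2.326 = 0.903, so 81.7%.

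The loss from 82.6% is under one point in each. A log-rank simulation with the SAP's piecewise hazards (uniform accrual assumed) gave a drop of about 0.2 points when 2% of subjects were censored at randomization. At 5% the drop was about 2 points. In the 3-month-delay case power stays at or above 99.9%.

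**The case against.** The strongest reply is that the tables do not say these deaths are dropped. The last row of each table counts them. The footnote on the first row of the primary table sets aside only deaths after subsequent therapy, which makes sense only if earlier deaths still matter there. The text rules and the protocol agree. Figures 4.1.2.1-1 and 4.1.2.2-1, which are also said to present the censoring rules, are not in the available text and may show the order of decisions. This reply stands against any claim that deaths are certainly lost. It does not remove the overlap, and the secondary table has no such footnote.

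A second reply is that few subjects can be affected. Protocol 3.3.1 calls for tumor imaging within 28 days before randomization. That is fair and limits the size, but the SAP still plans for missing baselines in two tables and two tabulations.

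A third is that affected subjects would be visible, because SAP 7.5.2.1 tabulates censoring reasons by arm and 7.5.2.2 provides a by-subject listing under both definitions. That helps an auditor find them but does not settle the rule. None of the 13 supportive PFS analyses in 7.5.2.2 tests it.

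A fourth is timing. According to the SAP document history, version 5.0 followed the first nivo+chemo PFS analysis, so rewriting the primary rule now would be a change after unblinding. This also stands, and it shapes the remedy for that analysis. The same definitions still govern nivo+ipi PFS (4.2.2.2, 7.5.3.5), the contribution-of-components analyses (8.1.1) and, through the primary-definition censoring rules, DOR (4.3.1).

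**Conclusion.** The first row of both PFS tables conflicts with the death row of the same table, with the SAP text rules and with protocol 8.3.1, and the available text states no precedence. This is a defect in the rule for a primary endpoint. Its likely numerical effect is small: about 3 to 14 of 841 to 857 events and under one point of power. That rests on an assumed 0.5% to 2% without a baseline, on average modelled mortality in those subjects, and on the first row always prevailing.

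A reader might infer three stronger things that the documents do not support:

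- **Every subject without a baseline is censored even after death.** The last row and the footnote point the other way, and the order actually programmed is unknown.
- **A scan done at site but unavailable or unreadable centrally triggers the row.** PFS is by BICR, but the documents do not say whether the row means a site or a central baseline.
- **The loss would differ by arm because the trial is open-label.** Baseline imaging is due before randomization and the central readers are blinded, so nothing in the documents suggests a mechanism.

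**What to change.** In both tables, reword the first row to: no baseline tumor assessment and no death. In the primary table, keep the footnote, so that the condition reads as no death before subsequent therapy. Deaths without progression then follow the death row. Align the censoring-reason labels in SAP 7.5.2.1 and 7.5.3.5, and apply the rule to the remaining PFS and DOR analyses. The cost is one line in each of two tables, two labels and a small derivation edit.

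For the completed nivo+chemo PFS analysis, leave the primary result as it is. State which row took precedence in the program, and report by arm the number of subjects without a baseline and how many of them died (before subsequent therapy, for the primary definition). If any of those deaths were censored, add a sensitivity analysis that counts them as events at the date of death. That requires one tabulation and at most one rerun per definition.
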